## 11.1. Primary Efficacy Analysis

### Intracranial Response Rate (IRR) in Cohort A

The intracranial response rate (IRR) is defined as the percentage of subjects achieving a confirmed intracranial CR or PR from the start of treatment until disease progression or the start of new anti-cancer therapy. This will be based on investigator-assessed best intracranial response.

Stable intracranial disease requires meeting the SD criteria at least once after the first dose of study treatment at a minimum interval of 8 weeks. As a window of  $\pm 7$  days is allowed for scheduling, 7 weeks (or 49 days) will be used for analysis.

To be assigned a status of intracranial PR or CR, a confirmatory disease assessment for intracranial disease should be performed not less than 4 weeks after the criteria for response are first met.

The Independent Reviewer-assessed best intracranial response will also be summarized.

Subjects with Not Evaluable (NE) or missing intracranial response will be treated as non-responders; i.e., they will be included in the denominator when calculating the percentage.

The exact 95% CI for the intracranial response rate will be calculated for both the interim and final analysis.

All data relating to intracranial response from the investigator and, if done, the independent reviewer will be listed, including lesion measurements, response assessments and best response.

A plot of the maximum percent tumor reduction in intracranial target lesions from baseline will be provided. The plot will be color-coded for best intracranial response. The subject number will be indicated on the plot.

Intracranial response will be determined using only intracranial target, non-target, and new lesions, using the criteria specified in the protocol.

Target Lesions	Non-Target Lesions	New Lesions	Intracranial Response
CR	CR or NA	No	CR
CR	Non-CR/Non-PD or NE	No	PR
PR	Non-PD or NA or NE	No	PR
SD	Non-PD or NA or NE	No	SD
NE	Non-PD or NA or NE	No	NE
PD	Any	Yes or No	PD
Any	PD	Yes or No	PD
Any	Any	Yes	PD

CR=complete response, PR = partial response, SD=stable disease, PD=progressive disease, NA= Not applicable, and NE=Not Evaluable

## 11.2. Secondary Efficacy Analyses

Intracranial Response (IR) in Cohorts B, C, and D

Intracranial response will be summarized for Cohorts B, C, and D as for Cohort A.

Extracranial Response (ER) in Cohorts A, B, C, and D

The extracranial response rate (ERR) is defined as the percentage of subjects achieving a confirmed extracranial CR or PR from the start of treatment until disease progression or the start of new anti-cancer therapy. This will be based on investigator-assessed best extracranial response.

Stable extracranial disease requires meeting the SD criteria at least once after the first dose of study treatment at a minimum interval of 8 weeks. To be assigned a status of extracranial PR or CR, a confirmatory disease assessment for extracranial disease should be performed not less than 4 weeks after the criteria for response are first met.

The Independent Reviewer-assessed best extracranial response will also be summarized.

Subjects with Not Evaluable (NE) or missing extracranial response will be treated as non-responders; i.e., they will be included in the denominator when calculating the percentage.

The exact 95% CI for the extracranial response rate will be calculated.

All data relating to extracranial response from the investigator and, if done, the independent reviewer will be listed, including lesion measurements, response assessments and best response.

A plot of the maximum percent tumor reduction in extracranial target lesions from baseline will be provided. The plot will be color-coded for best extracranial response. The subject number will be indicated on the plot.

Extracranial response will be determined using only extracranial target, non-target, and new lesions, using the criteria specified in the protocol.

Target Lesions	Non-Target Lesions	New Lesions	Extracranial Response
CR	CR or NA	No	CR
CR	Non-CR/Non-PD or NE	No	PR
PR	Non-PD or NA or NE	No	PR
SD	Non-PD or NA or NE	No	SD
NE	Non-PD or NA or NE	No	NE
PD	Any	Yes or No	PD
Any	PD	Yes or No	PD
Any	Any	Yes	PD

CR=complete response, PR = partial response, SD=stable disease, PD=progressive disease, NA= Not applicable, and NE=Not Evaluable

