**7.3.2.11. Evaluation of Best Intracranial, Extracranial and Overall Response**

The best intracranial, extracranial, and overall response is the best response recorded from the start of the treatment until intracranial, extracranial, and overall disease progression and will be determined programmatically by Novartis based on the investigators assessment of intracranial, extracranial, and overall response at each time point.

- To be assigned a status of intracranial, extracranial, overall stable disease (SD) follow-up disease assessment must have met the SD criteria at least once after first dose of study treatment at a minimum interval of 8 weeks.
- If the minimum time for SD is not met, best response will depend on the subsequent assessments. For example if an assessment of PD follows the assessment of SD and SD does not meet the minimum time requirement the best response will be PD. Alternatively subjects lost to follow-up after an SD assessment not meeting the minimum time criteria will be considered not evaluable.

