**Revision Chronology**

Date	Version
2015-FEB-10	Original
2017-FEB-23	Amendment No. 1
2018-MAR-05	Amendment No. 2

- 1) Minor correction to typographical errors throughout the document.
- 2) Title page: Updated description about study objective - to assess the intracranial response rate in subjects with locally confirmed BRAF V600E-mutation positive melanoma.
- 3) Section 2: Updated study objectives to be consistent with the study protocol amendment No.5 – 1. Primary endpoint amended to allow for locally confirmed BRAF V600E (followed by central confirmation as with all other cohorts) and 2. Secondary endpoint number 9: OS changed from 5 to 3 year.
- 4) Section 3: Updated Study design - Cohort A patient population updated to allow for locally confirmed BRAF V600E (followed by central confirmation as with all other cohorts) and definition of study closure updated from “where all subjects still in follow up have had at least 5 years follow up...” to “where all subjects still in follow up have had at least 3 years follow up...”.
- 5) Updated Protocol reference information from “Protocol Amendment 01, dated 27 April 2014 GlaxoSmithKline Document Number (2013N168168437\_01)” to “Protocol Amendment 05, dated 13 July 2016 GlaxoSmithKline Document Number (2013N168437\_07)”.
- 6) Section 4 and 4.2: reference to 5 year survival changed to 3.
- 7) Section 5.1: To clarify the significance level at the time of primary analysis, added “and the primary endpoint test in the primary analysis will be performed at 5% level”.
- 8) 
- 9) Added section 9.2.15 to clarify how to apply analysis cut-off date.
- 10) Section 10.3, 10.5 and 10.6: Updated the drug dictionary reference from “GSK Drug coding dictionary” to “WHODrug coding dictionary”.
- 11) Section 11.1: added “As a window of  $\pm 7$  days is allowed for scheduling, 7 weeks (or 49 days) will be used for analysis” to clarify the stable disease criteria.
- 12) As independent reviewer-assessment has been done, removed all the hypothetical wording (“If done”) removed.

- 13) Section 11.2: Added detailed derivation rules for the date of last contact.
- 14) Section 11.2: Added “The duration of intracranial, extracranial, and overall response per independent reviewer-assessment will also be summarized. Figures and listings of duration of independent reviewer-assessed response will also be provided.”.

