## Overall Response (OR) in Cohorts A, B, C, and D

The overall response rate (ORR) is defined as the percentage of subjects achieving a confirmed overall CR or PR from the start of treatment until disease progression or the start of new anti-cancer therapy. This will be based on investigator-assessed best overall response.

Stable disease requires meeting the SD criteria for both intracranial and extracranial disease at least once after the first dose of study treatment at a minimum interval of 8 weeks. To be assigned a status of overall PR or CR, a confirmatory disease assessment for both intracranial and extracranial disease should be performed not less than 4 weeks after the criteria for response are first met.

The Independent Reviewer-assessed best overall response will also be summarized.

Subjects with Not Evaluable (NE) or missing overall response will be treated as non-responders; i.e., they will be included in the denominator when calculating the percentage.

The exact 95% CI for the overall response rate will be calculated.

All data relating to overall response from the investigator and, if done, the independent reviewer will be listed, including lesion measurements, response assessments and best response.

A plot of the maximum percent tumor reduction in overall target lesions from baseline will be provided. The plot will be color-coded for best overall response. The subject number will be indicated on the plot.

Overall response will be determined using both extracranial and intracranial target, non-target, and new lesions, using the criteria specified in the protocol. Overall target lesion response is based on all (that is, intracranial and extracranial) target lesions, up to 10 total. The sum of longest diameters of all intracranial and extracranial target lesions will be used to determine overall response. Unequivocal new intracranial or extracranial (or both) lesions, or unequivocal intracranial or extracranial (or both) non-target lesion progression indicate overall progression. Target, non-target, and new lesion responses are combined as for intracranial and extracranial response to determine response at each disease assessment and best overall response.

- Complete Response (CR): Disappearance of all intracranial and extracranial target lesions. Any pathological lymph nodes must be <10mm in the short axis.

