#### Intracranial, Extracranial, and Overall Disease Control in Cohorts A, B, C, and D

The intracranial disease control (IDC), extracranial disease control (EDC), and overall disease control (ODC) are defined as CR+PR+SD for intracranial, extracranial, and overall disease control, respectively. Disease control rates are defined as the percentage of subjects achieving a confirmed overall CR or PR, or SD for at least 8 weeks from the start of study treatment, from the start of treatment until disease progression or the start of new anti-cancer therapy. This will be based on investigator-assessed responses.

The Independent Reviewer-assessed disease control rate will also be summarized.

Subjects with Not Evaluable (NE) or missing intracranial, extracranial, or overall response will be treated as non-responders; i.e., they will be included in the denominator when calculating the percentage.

Exact 95% CIs for the disease control rates will be calculated.

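### The SAP uses a 49-day minimum for intracranial stable disease but 8 weeks for extracranial, overall and disease control, so intracranial disease control has two minimums

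*SAP*

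**What the plan says.** **Intracranial SD, 49 days.** SAP 11.1 gives a nominal 8-week minimum and then replaces it for analysis, citing the ±7-day scheduling window: "7 weeks (or 49 days) will be used for analysis". SAP 11.2 extends this beyond Cohort A: "Intracranial response will be summarized for Cohorts B, C, and D as for Cohort A".

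**Everything else, 8 weeks.** SAP 11.2 has three further rules, none with an allowance:

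- Extracranial: "Stable extracranial disease requires meeting the SD criteria at least once after the first dose of study treatment at a minimum interval of 8 weeks".
- Overall: "Stable disease requires meeting the SD criteria for both intracranial and extracranial disease at least once after the first dose of study treatment", again at a minimum interval of 8 weeks.
- Disease control, one paragraph for intracranial, extracranial and overall (IDC, EDC, ODC): confirmed CR or PR, "or SD for at least 8 weeks from the start of study treatment".

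**Amendment log.** Item 11 of the SAP Revision Chronology lists the 49-day sentence under Section 11.1 and says it was added "to clarify the stable disease criteria".

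**Protocol.** Section 7.3.2.11 sets one 8-week minimum for all three response types: "To be assigned a status of intracranial, extracranial, overall stable disease (SD) follow-up disease assessment must have met the SD criteria at least once". If the minimum is missed, later assessments decide: "if an assessment of PD follows the assessment of SD and SD does not meet the minimum time requirement the best response will be PD". A subject lost to follow-up after a too-early SD becomes not evaluable (NE).

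**The concern.** The reason given for 49 days is the scan window, and that reason is not specific to the brain. Protocol Table 19 (footnotes 1, 21 and 22) and SAP Section 3 give intracranial and extracranial scans the same schedule, and the ±7 days in footnote 1 covers all scans. The protocol also has a single minimum. Nothing in either document explains why only intracranial SD should get the allowance.

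Two inconsistencies follow. First, identical scan timing can yield SD in the best intracranial response table and PD or NE in the extracranial and overall tables. Second, SAP Section 2 defines IDC as CR plus PR plus SD for intracranial disease, so a subject whose best intracranial response is SD should count. Under the disease control paragraph the same subject can fail. The best-response table and the IDC rate might then not reconcile.

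IDC, EDC and ODC are secondary endpoints in all four cohorts, reported for the investigator and the independent reviewer.

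**Working it through.** **Inputs.** SD minimum: 49 days for best intracranial response (SAP 11.1); 8 weeks = 56 days for extracranial SD, overall SD and disease control (SAP 11.2). Scan window: ±7 days (Protocol Table 19 footnote 1; SAP 11.1). Day count: date minus treatment start plus 1 (SAP 9.2.1, 9.2.3, 9.2.4). Cohort sizes: 75, and 15 for a smaller cohort (Cohort C is up to 15). Assumption: Week 8 means 56 days after first dose.

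**1. The plan's own figure.** 8 × 7 − 7 = 49 days = 7 weeks. It reproduces.

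**2. Permitted Week 8 scan dates.** 56 ± 7 gives date differences of 49 to 63, which is 15 dates.

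| Counting rule | Range | Below 56 | Below 49 |
|---|---|---|---|
| SAP count (difference + 1) | 50-64 | 50-55: 6 of 15 (40.0%) | 0 |
| Simple date difference | 49-63 | 49-55: 7 of 15 (46.7%) | 0 |
| Week 8 taken as Study Day 56 | 49-63 | 49-55: 7 of 15 | 0 |

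These are shares of permitted dates, not of subjects.

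**3. Who changes category.** The next scheduled scan is Week 16. A category changes only for a subject with no confirmed response, SD on an early-window Week 8 scan, and PD or loss to follow-up before any later qualifying assessment. A later unconfirmed CR or PR can also support SD (Protocol 7.2.2).

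Take such a subject, with SD at a date difference of 50 (SAP count 51) and PD at Week 16:

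- Best intracranial response: 51 ≥ 49, so SD.
- IDC under the disease control paragraph: 51 < 56, so not controlled.
- The same timing for extracranial or overall SD: 51 < 56, so best response is PD (NE if lost to follow-up instead).

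**4. Effect per subject.** 1/75 = 1.33 points in Cohort A; 1/15 = 6.67 points in a cohort of 15. With assumed counts, 12/15 = 80.0% (exact 95% CI 51.9 to 95.7) becomes 11/15 = 73.3% (44.9 to 92.2).

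**5. Range for Cohort A, on assumptions only.** Let q be the share of subjects whose last SD is at Week 8 and e the share of those scans that are early. Affected subjects = 75 × q × e. With q from 5% to 20% and e from 10% to 7/15 (the last treating all permitted dates as equally likely):

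- low: 75 × 0.05 × 0.10 = 0.4 subjects (0.5 points)
- high: 75 × 0.20 × 7/15 = 7.0 subjects (9.3 points)

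Neither q nor e is in the documents.

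**The case against.** The strongest reply is that 49 days is the working meaning of 8 weeks throughout. SAP 11.1 also begins with 8 weeks and only then says how it is applied; the log speaks of the SD criteria in general; the protocol has one rule. On that reading the disease control wording is shorthand for the same minimum. A programmer could reasonably take it so, but no sentence in the SAP says it. The allowance sits only in the intracranial section, and the log files it there. Where the SAP wants window relief elsewhere, it writes it out: the PFS rule in 9.2.11 uses 16 weeks plus 7 days = 119 days.

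SAP 9.2 also refers to separate dataset specifications, which are not available here. They may already use one constant, but they should implement the SAP text, not override it.

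The date count can be challenged too, because Protocol 7.2.2 gives a ±3-day window for post-baseline assessments. That point stands. Under it there are 7 permitted dates, of which 2 fall short of 56 on the SAP count (54-60) and 3 by simple difference (53-59). The count is smaller, but the conflict remains, and SAP 11.1 itself adopts ±7 days.

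Finally, the effect is narrow and descriptive. That also stands, and it limits the weight of the point.

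**Conclusion.** The concern holds. Read as written, the SAP gives IDC two different SD minimums and treats extracranial and overall SD differently from intracranial SD without a reason. Up to 6 of 15 permitted Week 8 dates (SAP count, ±7-day window, Week 8 at 56 days) lie between the two rules. How many subjects fall there is unknown; each is worth 1.3 points in Cohort A and 6.7 points in a cohort of 15.

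The reach is limited to the SD/PD/NE split of best response and the disease control rates. The primary intracranial response test, sample size, confirmed response rates, PFS, OS and duration of response do not use the SD minimum. It should be corrected, but it does not threaten the trial's main conclusion.

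**What to change.** State one SD minimum, in days and with its day-count convention, and apply it to intracranial, extracranial and overall SD and to the disease control definition, for both investigator and independent-reviewer tables.

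- **Preferred:** extend the 49-day allowance to the extracranial, overall and disease control paragraphs of SAP 11.2. The reason in 11.1 applies equally there, and it matches the 7-day allowance in the PFS rule. Record it as a departure from the protocol's 8 weeks in the SAP and study report, as Protocol 9.3.5 requires.
- **Alternative:** delete the 49-day sentence from SAP 11.1 and keep 8 weeks everywhere.

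In either case, reconcile the ±7-day window in Table 19 with the ±3 days in Protocol 7.2.2, since the 49 days depends on it.

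The SD rule itself costs one to three SAP sentences, one programming constant and, for 49 days, a short note of the departure. No new data are needed. SD counts and disease control rates may shift slightly.

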## Overall Response (OR) in Cohorts A, B, C, and D

The overall response rate (ORR) is defined as the percentage of subjects achieving a confirmed overall CR or PR from the start of treatment until disease progression or the start of new anti-cancer therapy. This will be based on investigator-assessed best overall response.

Stable disease requires meeting the SD criteria for both intracranial and extracranial disease at least once after the first dose of study treatment at a minimum interval of 8 weeks. To be assigned a status of overall PR or CR, a confirmatory disease assessment for both intracranial and extracranial disease should be performed not less than 4 weeks after the criteria for response are first met.

The Independent Reviewer-assessed best overall response will also be summarized.

Subjects with Not Evaluable (NE) or missing overall response will be treated as non-responders; i.e., they will be included in the denominator when calculating the percentage.

The exact 95% CI for the overall response rate will be calculated.

All data relating to overall response from the investigator and, if done, the independent reviewer will be listed, including lesion measurements, response assessments and best response.

A plot of the maximum percent tumor reduction in overall target lesions from baseline will be provided. The plot will be color-coded for best overall response. The subject number will be indicated on the plot.

Overall response will be determined using both extracranial and intracranial target, non-target, and new lesions, using the criteria specified in the protocol. Overall target lesion response is based on all (that is, intracranial and extracranial) target lesions, up to 10 total. The sum of longest diameters of all intracranial and extracranial target lesions will be used to determine overall response. Unequivocal new intracranial or extracranial (or both) lesions, or unequivocal intracranial or extracranial (or both) non-target lesion progression indicate overall progression. Target, non-target, and new lesion responses are combined as for intracranial and extracranial response to determine response at each disease assessment and best overall response.

- Complete Response (CR): Disappearance of all intracranial and extracranial target lesions. Any pathological lymph nodes must be <10mm in the short axis.
- Partial Response (PR): At least a 30% decrease in the sum of the diameters of intracranial and extracranial target lesions, taking as a reference, the baseline sum of the intracranial and extracranial diameters (e.g. percent change from baseline).
- Stable Disease (SD): Neither sufficient shrinkage to qualify for PR nor sufficient increase to qualify for progressive disease.
- Progressive Disease (PD): At least a 20% increase in the sum of the diameters of intracranial and extracranial target lesions, taking as a reference, the smallest sum of intracranial and extracranial diameters recorded since the treatment started (e.g.,

percent change from nadir, where nadir is defined as the smallest sum of diameters recorded since treatment start). In addition, the sum must have an absolute increase from nadir of 5mm.

- Not Evaluable (NE): Cannot be classified by one of the five preceding definitions.

#### Intracranial, Extracranial, and Overall Disease Control in Cohorts A, B, C, and D

The intracranial disease control (IDC), extracranial disease control (EDC), and overall disease control (ODC) are defined as CR+PR+SD for intracranial, extracranial, and overall disease control, respectively. Disease control rates are defined as the percentage of subjects achieving a confirmed overall CR or PR, or SD for at least 8 weeks from the start of study treatment, from the start of treatment until disease progression or the start of new anti-cancer therapy. This will be based on investigator-assessed responses.

The Independent Reviewer-assessed disease control rate will also be summarized.

Subjects with Not Evaluable (NE) or missing intracranial, extracranial, or overall response will be treated as non-responders; i.e., they will be included in the denominator when calculating the percentage.

Exact 95% CIs for the disease control rates will be calculated.

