## 2. STUDY OBJECTIVES AND ENDPOINTS

Objectives	Endpoints
Primary	

 
To assess the intracranial response (IR) of subjects with locally confirmed BRAF V600E-mutation positive melanoma that has metastasized to the brain without symptoms and have not undergone prior local therapy for brain metastases, ECOG score of 0-1 (Cohort A).
 
	
 
IR is defined as the proportion of subjects with a confirmed intracranial complete response (CR) or partial response (PR) as per investigator assessment using modified RECIST 1.1 guidelines.
 

Secondary	

 
To assess cohort B for IR of subjects with locally confirmed BRAF V600E cutaneous melanoma with metastases to the brain confirmed by MRI, asymptomatic with prior local therapy for brain metastases; ECOG score of 0-1.
 
To assess cohort C for IR of subjects with locally confirmed BRAF V600 D/K/R cutaneous melanoma with metastases to the brain confirmed by MRI, asymptomatic, with or without prior local therapy; ECOG score of 0-1.
 
To assess cohort D for IR of subjects with locally confirmed BRAF V600 D/E/K/R cutaneous melanoma with metastases to the brain confirmed by MRI, symptomatic; with or without prior local therapy; ECOG score of 0-2.
 
	
 
IR is defined as the percentage of subjects with a confirmed intracranial complete response (CR) or partial response (PR) as per investigator assessment using modified RECIST 1.1 guidelines.
 

Objectives	Endpoints

4. To assess Cohorts A, B, C and D for Disease Control for intracranial, extracranial and overall response (IDC, EDC and ODC respectively)
	
 
• Intracranial Disease Control (IDC) is defined as CR+PR+SD for intracranial disease
 
• Extracranial Disease Control (EDC) is defined as CR+PR+SD for extracranial disease
 
• Overall Disease Control (ODC) is defined as CR+PR+SD for overall disease
 

5. To assess Cohorts A, B, C and D for extracranial response rate (ER)
	
 
• Extracranial response (ER), defined as the percentage of subjects with a best extracranial response of a confirmed CR or PR by investigator assessment using modified RECIST 1.1
 

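### SAP 11.2 gives conflicting rules for disease control: one overall-response numerator serves all three rates, and overall SD is tied to both compartments despite a pooled-sum definition

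*SAP*

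**What the plan says.** **Disease-control rates.** Section 2 of the SAP gives each rate its own definition, for example "Intracranial Disease Control (IDC) is defined as CR+PR+SD for intracranial disease" and "Extracranial Disease Control (EDC) is defined as CR+PR+SD for extracranial disease", with ODC worded in the same way. The disease-control paragraph of 11.2 opens consistently with this: the three quantities "are defined as CR+PR+SD for intracranial, extracranial, and overall disease control, respectively". The sentence straight after it, which defines the percentage to be reported, reads "Disease control rates are defined as the percentage of subjects achieving a confirmed overall CR or PR, or SD for at least 8 weeks". It names no compartment for SD. The paragraph's rule for missing data then returns to separate responses: "Subjects with Not Evaluable (NE) or missing intracranial, extracranial, or overall response will be treated as non-responders".

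**Overall SD.** The overall-response paragraph of 11.2 says "Stable disease requires meeting the SD criteria for both intracranial and extracranial disease at least once after the first dose of study treatment"; an 8-week minimum applies. The same paragraph bases overall response on the summed diameters of all intracranial and extracranial target lesions, and its category list defines overall SD as "Neither sufficient shrinkage to qualify for PR nor sufficient increase to qualify for progressive disease". Protocol 7.3.2.5 also uses the pooled sum with SD as the residual category. Protocol 7.3.2.11 sets the 8-week minimum for each response type and does not ask for SD in both compartments. Intracranial SD (SAP 11.1) and extracranial SD (SAP 11.2) have their own single-compartment rules.

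**The concern.** There are two separate faults, and they affect different rates.

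1. The sentence that defines the reported rate uses overall CR or PR for all three. That is correct for ODC. For IDC and EDC it contradicts the sentence before it and Section 2.
2. The both-compartment condition for SD contradicts the pooled-sum definition of overall SD in the same section. It affects ODC.

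Disease control is a listed secondary endpoint in every cohort, reported with exact 95% confidence intervals by investigator and by independent reviewer. Protocol 1.1.1 and 1.2 quote IDC from the earlier dabrafenib study, so readers will look at IDC as a brain-specific figure. Two programmers working from 11.2 could produce different counts and both be following the text.

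**Working it through.** The documents give no expected value, power or threshold for IDC, EDC or ODC, so there is no planned figure to reproduce. The check applies the documents' own thresholds to assumed lesion sums.

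**Inputs.**
- PR: a fall of at least 30% from baseline. PD: a rise of at least 20% and 5 mm from nadir. SD: anything between (protocol 7.3.2.1, 7.3.2.3, 7.3.2.5; SAP 11.2).
- Confirmation at least 4 weeks after first response; scans at Week 4 and Week 8.
- Cohort sizes 75, 15, up to 15, and 15 (protocol 4.1.1).
- Assumed for cases 1 to 4: baseline is the nadir, status holds for 8 weeks or more, responses are confirmed, and there are no new lesions and no non-target progression.

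Percent change = (new sum − old sum) / old sum.

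| Case | Intracranial (mm) | Extracranial (mm) | Pooled (mm) |
|---|---|---|---|
| 1 | 80 to 40: −50%, PR | 20 to 26: +30%, +6 mm, PD | 100 to 66: −34%, PR |
| 2 | 20 to 26: +30%, +6 mm, PD | 80 to 40: −50%, PR | 100 to 66: −34%, PR |
| 3 | 20 to 12: −40%, PR | 100 to 85: −15%, SD | 120 to 97: −19.2%, SD |
| 4 | 20 to 13: −35%, PR | 60 to 75: +25%, +15 mm, PD | 80 to 88: +10%, SD |

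**Fault 1, the rate sentence (IDC and EDC).**
- Case 1: by compartment, EDC is no. Taken literally, the subject has a confirmed overall PR, so EDC is yes.
- Case 2, the mirror image: by compartment, IDC is no. Taken literally, IDC is yes.
- A timing case in the other direction: intracranial PR at Week 4 and again at Week 8, with a new extracranial lesion at Week 8. The intracranial PR is confirmed, so IDC is yes by compartment. Overall response at Week 8 is PD. There is no confirmed overall CR or PR, and no response type is in the SD category at 8 weeks. Taken literally, IDC is no.

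**Fault 2, the both-compartment SD rule (ODC).**
- Case 3: pooled response is SD, so ODC is yes under the category list and protocol 7.3.2.5. Under the both-compartment sentence the brain meets PR rather than SD, so overall SD is not assigned and ODC is no, although neither compartment has progressed.
- No extracranial disease: eligibility requires only a measurable intracranial lesion (protocol 4.1.2, criterion 6), and protocol 7.3.2.5 foresees subjects with no extracranial target lesions. The both-compartment sentence does not say how such a subject reaches overall SD.

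**Size.** One subject is 1/75 = 1.3 points in Cohort A and 1/15 = 6.7 points in a cohort of 15. The number affected is unknown, so the following counts are assumptions, with exact 95% intervals:

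| Counted as controlled | Rate | 95% CI |
|---|---|---|
| 60/75 | 80.0% | 69.2 to 88.4 |
| 56/75 (4 fewer) | 74.7% | 63.3 to 84.0 |
| 52/75 (8 fewer) | 69.3% | 57.6 to 79.5 |
| 12/15 | 80.0% | 51.9 to 95.7 |
| 11/15 (1 fewer) | 73.3% | 44.9 to 92.2 |

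**The case against.** The case for leaving the text alone is that the right definition is already there. Section 2 states it, the opening sentence of the paragraph repeats it with *respectively*, and the missing-data rule names the three responses separately. The phrase about confirmed overall CR or PR also appears in the overall response rate definition, so it is probably a carry-over. SAP 9.2 leaves full derivations to dataset specifications that are not among these documents, and SAP 14.1.1 lists separate intracranial, extracranial and overall best-response tables. This stands, and it limits the claim: a reader might infer that the SAP defines all three rates by overall response and that all three will be miscounted, and the documents do not show that. What is left is that the sentence defining the reported percentage disagrees with its neighbours and nothing says which governs.

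On overall SD, the both-compartment sentence can be read as a floor, meaning at least SD in each compartment for the minimum time. Protocol 7.2.2 lends some support, since an unconfirmed CR or PR may fall back to SD. On that reading case 3 stays in ODC. The reading still does not match the pooled rule: in case 4 pooled response is SD, yet the extracranial compartment has progressed and fails the floor. Nor does it settle subjects without extracranial disease. For them the gap is unstated handling; it would go too far to say the SAP excludes them.

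A reader might also size the error from the earlier dabrafenib study: IDC of 81.1% and 89.2% (protocol 1.1.1) against overall disease control of 80% and 83% (Protocol Summary), gaps of 1.1 and 6.2 points. That does not measure this fault. It comes from another trial, the Summary uses *overall* loosely (it also speaks of an overall intracranial response rate), and the literal rate sentence is not ODC either, because its SD has no compartment.

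**Conclusion.** SAP 11.2 contradicts itself on disease control in two places. The rate sentence, programmed literally, can misclassify subjects for IDC and EDC in either direction; it is correct for ODC. The both-compartment SD sentence, read literally, can remove subjects with brain PR, body SD and pooled SD from ODC, and leaves subjects without extracranial disease with no stated route to overall SD.

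The effect is 1.3 points per subject in Cohort A and 6.7 points per subject in a cohort of 15. The total cannot be given, because neither the number of discordant subjects nor the programmed derivation is in the documents. The worked cases rest on assumed lesion sums and show only that the readings diverge. These are descriptive secondary endpoints without a hypothesis test, and the primary intracranial response analysis in Cohort A does not depend on them. The wording should be corrected before the rates are produced.

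**What to change.** Three changes to SAP 11.2:

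1. In the disease-control paragraph, replace the numerator in the second sentence with: *a confirmed CR or PR, or SD for at least 8 weeks, in the respective response (intracranial for IDC, extracranial for EDC, overall for ODC)*.
2. In the overall-response paragraph, define overall SD as the pooled overall response (the SAP's own category list; protocol 7.3.2.5, 7.3.2.10 and 7.3.2.11) meeting SD at the minimum interval, and delete the condition that both compartments meet SD.
3. State that for subjects with no extracranial disease at baseline, overall response rests on intracranial disease plus any new lesions. Apply this also to the next sentence of that paragraph, which asks for a confirmatory assessment of both compartments before overall CR or PR.

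The cost is SAP wording and a check that the dataset specifications agree. No new data are needed, and neither the sample size nor the primary analysis changes.
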